10. STATISTICAL ANALYSIS PLAN

Statistical analysis will be performed by tenured [name] in Biostatistics. [name] is involved in all statistical aspects of our lab including power calculations, secure data storage, data synthesis/ interpretation and guidance regarding analytical/quantitative techniques. In addition, we encourage all junior members of our laboratory to gain proficiency in analytical methods such that investigators emerge from the laboratory with both biological as well as statistical skills. [name] is eager to help mentor our junior members to ensure that these goals are achieved. [name] has developed an interest in sleep science through our interactions and is a strong member of our team. In all cases we are adequately powered to assess the impact of sex as a biological variable which will be an important exploratory goal of our study, given known sex differences in sleep disorders, Alzheimer's, and tau. Moreover, we are careful to control for various covariates including age, gender, BMI and ApoE status (which is part of the PHS score). We recognize that ApoE status may be a risk factor for OSA as well as AD and may have complex interactions with OSA effects on memory, making careful analyses of interactions important.

Aim 1: Although all major pathophysiological traits will be assessed, our primary outcome is to compare the loop gain of older OSA patients (age 65-85 years) with the loop gain of carefully matched individuals without

OSA. We will assess our predictors of oxygen responsiveness to extend our recent publications⁵⁰. We have powered this analysis using our preliminary data based on a mean loop gain difference of 2.1 with standard deviation 0.4 using an unpaired t test with $\alpha=0.05$ and $\text{power}>0.8$. We will also analyze age as a continuous variable within the 20 year range. Our sample size will be adequate to adjust for any covariates (if matching is inadequate or other relevant covariates are imbalanced) and will provide participants for the other aims in which oxygen responsive OSA patients are required. We will also model the various pathophysiological traits (as previously described²⁶⁰) to determine how loop gain, upper airway gain, arousal threshold, and pharyngeal anatomy interact¹³⁵. This aim will provide a rich data set for further analyses/signal processing^{250,251,262,263} and characterizing thoroughly participants in the subsequent aims. For **Aim 2**, we will quantify the apnea hypopnea index (using criteria independent of desaturation) on 2 l/min supplemental O₂ vs sham (room air) in patients with varying underlying endotypes. We have powered this analysis based on our preliminary data using a $\text{power}>0.8$ and $\alpha=0.05$ with a change in AHI of 20/h (a clinically important difference) with standard deviation 5/h. We will also assess changes in neurocognitive function (Aim 2, VPA primary neurocognitive outcome).

The interpretation should be straightforward. If we confirm a major subset of OSA patients who are oxygen responsive, we will extend our recent findings that we can identify these patients based on underlying pathophysiology. If oxygen therapy lowers both loop gain and AHI then this finding would support our assertion that loop gain is causally important in a subset of OSA patients and that oxygen is a viable therapeutic approach.

If loop gain is not lowered with oxygen then we would conclude either the dose/duration of oxygen was inadequate or that the elevated loop gain is an intrinsic/irreversible property of OSA. If loop gain is lowered, but AHI is not improved, this finding might support the notion that elevated loop gain is either a consequence or an epiphenomenon in OSA but not causally important in these patients³¹¹. Clearly the changes in loop gain will be interpreted in the context of other endotypes, given that loop gain per se was not predictive of O₂ response in our recent study. Rather, the combination of endotypes determined oxygen response with 83% accuracy in our pathophysiological model which we are working to validate further. [name] (Co-I), neuropsychologist will oversee cognitive assessment and impact of treatment on memory. We anticipate improvement in memory consolidation although we recognize a single night of therapy may be inadequate to see important changes. We have previously observed subjective without objective improvements in brain function with overnight therapy, leading us to speculate that the initial improvement with OSA therapy may be an "illusion"³¹².

Aim 3: We have powered this aim based on the literature, our experience and that of our imaging collaborators. The techniques to acquire structural images of the brain are well established, but the sensitivity of these techniques to changes induced by alleviating hypoxemia/OSA is less clear. Although we have chosen hippocampal volume as our primary measure (outcome)²⁰⁰, we will assess other brain regions for possible use in future studies. We will further quantify beta-amyloid neuritic plaque density and tau protein using PET scanning to assess the impact of OSA on predictors of AD. We will focus on the hippocampus and medial temporal lobe and other regions showing evidence of tau accumulation in the preclinical phase^{313,314}. Given the multiple comparisons inherent in our exploratory aim assessing the entire brain, we are not powered for brain structures beyond our primary outcomes. Based on our prior work, with $n=20$ per group, we have $\text{power}>80\%$ with $\alpha=0.05$ to find a hippocampal volume difference of 0.3 vs. 0.4 (as %ICV – intracranial cavity volume) with $\text{SD}=0.03$ which is a clinically important difference i.e. associated with measurable memory differences²⁰⁰. For amyloid PET imaging, with $n=20$ per group, we will have $>80\%$ power with $\alpha=0.05$ assuming $\text{SUVr}=1.53$ ($\text{SD}=0.18$) to show a clinically important difference of 0.2 between OSA and matched non-OSA³¹⁵. Further, we will use the preliminary data obtained from this aim to design further rigorous brain imaging studies in the future.

The interpretation of this aim will be based primarily on the hippocampal outcomes and the amyloid and tau quantification. [name] (Co-I) is a neuroimaging expert who will oversee these analyses with [name]

[name], PhD, who is an expert neuropsychologist. We anticipate that we will see smaller hippocampal volume in OSA vs. controls although this finding will depend to some extent on the magnitude of the memory impairment in Aim 2. Our use of amyloid and tau quantification will be of major interest given the novelty in OSA. We expect the extent of tau within the region of interest to be higher in participants with OSA. We will also explore how tau relates to improvement of learning with OSA therapy. We are also optimistic that beta-amyloid neuritic plaque density may be a robust outcome metric for future longitudinal studies. We can clearly determine how various neurocognitive abnormalities correspond with MR and PET findings^{184,316,317}.

Aim 4: [name] our Co-I Tenured [name] will oversee these analyses for our pilot clinical trial although the PI and the Co-Is (including [name] for AD) have considerable clinical trial experience as well. We will compare the results of the word pairs test with 3 months of O2 vs. PAP therapy (n=60 total completing). We will use an intention to treat analysis such that all randomized patients will be included and any dropouts will be analyzed using last observation carry forward. We powered this analysis based on our preliminary data with a treatment related difference of 6.9% (a clinically relevant difference) and sd=2.2% assuming alpha=.05 and power>0.8. Although we will compare O2 to PAP, we will also assess within-subject changes with treatment. For treatment, we will perform an efficacy analysis since we anticipate that despite our best efforts adherence will be imperfect. We will analyze other neurocognitive variables as well in an exploratory manner, but are not powered for multiple comparisons. We will also compare preferences with therapy via structured exit interviews to understand how best to optimize a large multicenter comparative effectiveness trial if our results are indeed compelling^{318,319}. We will adjust for covariates (eg. age, BMI, sex, PHS score) if imbalanced after randomization.

Several possibilities exist for our findings from this aim. Oxygen may be superior to PAP which would pave the way for multicenter comparative effectiveness trials which could change the current standard of care for selected patients²⁹¹. Oxygen could be equivalent to PAP which could reflect reality or could imply that our studies are underpowered, or that the word pairs test is insufficiently sensitive to treatment differences, or perhaps the dose/duration of therapy was inadequate. Of note, we will be able to analyze the data examining various subsets based on underlying pathophysiology. Another possibility is that oxygen improves the AHI but not the corresponding tests of neurocognitive function. Such a finding might point to irreversible effects of apnea or perhaps inadequate statistical power. We will clearly be in a position to assess whether treatment is simply making the numbers look better or actually improving the health of the patient. Because we regard Aim 4 as a pilot study, we will also independently analyze the oxygen effect and the PAP effect to design future studies.

We work closely with [name] (Co-I) who leads the IBM cohort and is very focused on healthy aging. One of the corollaries of identifying predictors of memory impairment will be to identify markers/predictors of healthy aging e.g. absence of OSA may identify healthy elderly people without neurocognitive impairment. Based on the substantial data acquired through the proposed studies, we will be in good position with our statistical team to create a multivariate model to assess predictors of healthy aging, of major clinical relevance.

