11. HUMAN SUBJECTS

We will enroll 260 participants for the protocol.

Aim 1— Overnight Visit #1

We anticipate that 130 subjects will complete Overnight visit #1.

Aim 2 — Overnight Visit #2 and #3

Of the 130 subjects that complete Aim 1, 65 subjects who have been identified to have obstructive sleep apnea will complete Overnight visit #2-#3.

Aim 3 — Imaging Visit #1

Of the 20 subjects that complete Aim 1 and Aim 2, the same participants will be invited to complete Imaging

Visit #1. We will attempt to enroll all 20 subjects. Additionally, 20 subjects without OSA, who completed overnight visit 1, will be invited to complete the imaging visit. In total, we will recruit 40 subjects for this aim.

Aim 4 — 3 month Trial of Supplemental O2 or PAP therapy

Of the 130 subjects that completed Aim 1, 60 obstructive sleep apnea oxygen sensitive subjects will be invited to complete a 3-month trial of supplemental oxygen or PAP therapy. Subjects that complete the trial will return for Morning Visit 1.

[figure not shown]

Figure 3. Schematic of study visits and participants to be enrolled per aim.

Inclusion:

1. Age 65-85 years
2. Gender: Men or Women
3. MOCA > 26
4. Independently living and able to drive
5. OSA (AHI \geq 5/h) or no OSA
6. Subjects must consent to waiving their right to obtain their PHS score (since the score is not yet actionable and could lead to social stress and ethical dilemmas)

Exclusion:

1. Currently smoking
2. History of COPD or asthma
3. Heart Failure Class III or IV, unstable cardiovascular disease, or uncontrolled hypertension
4. Neuromuscular Disease
5. Drowsy Driving (ESS > 18/24)
6. Inability to complete study procedures, such as questionnaire that are only available/validated in English
7. Lack of decisional capacity to provide informed consent
8. Participants in whom magnetic resonance imaging Magnetic Resonance Imaging [MRI] is contraindicated including, but not limited to, those with a pacemaker, presence of metallic fragments

near the eyes or spinal cord, or cochlear implant

9. Presence of a brain tumor or lobar stroke
10. Current drug or alcohol abuse/dependence
11. Prisoners

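### The statement that every aim is adequately powered for sex has no calculation behind it and fails for Aim 3 amyloid PET on the plan's own inputs (minor)

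*Combined protocol and SAP*

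**What the plan says.** The opening paragraph of Section 10 (Statistical Analysis Plan) makes a claim covering all aims: "In all cases we are adequately powered to assess the impact of sex as a biological variable". The sentence goes on to label this goal exploratory. The same paragraph remarks that ApoE may interact with OSA effects on memory, "making careful analyses of interactions important". It does not say whether the impact of sex means a main effect, effects within each sex, or effect modification.

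The power statements that follow each size one overall comparison: loop gain in Aim 1, AHI in Aim 2, hippocampal volume and amyloid SUVr in Aim 3, and word pairs in Aim 4. None gives a sex effect, a sex split or an interaction. The amyloid statement begins "For amyloid PET imaging, with $n=20$ per group" and claims more than 80% power at alpha 0.05 for a difference of 0.2 with SD 0.18. Tau PET is also part of Aim 3 but has no power figure.

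Section 11 (Human Subjects) makes both sexes eligible without a quota or stratification, and confirms the Aim 3 total: "In total, we will recruit 40 subjects for this aim".

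**The concern.** A claim covering every case is defeated by one counterexample. A sample that comfortably detects an overall difference may still be too small to detect the same difference within each sex. It is weaker again for the contrast between the sexes: with an even split, the interaction has twice the standard error of the overall comparison. Amyloid PET is where this matters, because it combines the smallest sample with the smallest standardised effect among the plan's power statements.

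What is at stake is interpretation. If the plan says it is adequately powered for sex, a non-significant sex interaction on amyloid could later be reported as evidence of no sex difference. The plan does not propose to do this, but the sentence would seem to license it.

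**Working it through.** **Inputs.** From Section 10, Aim 3: amyloid difference 0.2 SUVr, SD 0.18, 20 per group, alpha 0.05. From Section 11: 40 in total. Assumptions: two-sided tests (the plan does not state sidedness), a common SD, and 10 men and 10 women in each group. Power is from the noncentral t distribution.

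**1. The plan's own figure.** Standardised difference 0.2/0.18 = 1.11. SE = 0.18 × √(2/20) = 0.0569, noncentrality 0.2/0.0569 = 3.51, 38 df. Power is 92.8%, consistent with the stated figure of more than 80%.

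**2. OSA effect within one sex (10 vs 10).** SE = 0.18 × √(2/10) = 0.0805, noncentrality 2.48, 18 df. Power is **65.2%**. Variants: 67.6% with the error pooled over both sexes (36 df), 70.0% by normal approximation, 77.2% with a one-sided t test and 79.9% with a one-sided normal approximation. All are below 80%.

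**3. Sex-by-OSA interaction of 0.2 SUVr.** SE = 0.18 × √(4/10) = 0.1138, noncentrality 1.76, 36 df. Power is **40.1%**. For an interaction of 0.1 it is 13.7%.

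**4. Precision.** The 95% CI half-width for the interaction is 2.03 × 0.1138 = **0.23 SUVr**. The smallest interaction detectable with 80% power is about 0.33 SUVr.

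**5. Size needed for 80% power.** Within sex: 14 per sex per group, 14 × 4 = 56 in total. Interaction of 0.2: 26 per sex per group, 26 × 4 = 104 in total. The plan has 40.

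**6. Sensitivity to the sex split (same split in both groups).**

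| Smaller sex, per group | Power in smaller sex | Interaction power |
|---|---|---|
| 10 | 65% | 40% |
| 8 | 54% | 39% |
| 6 | 41% | 35% |
| 4 | 26% | 28% |

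The even split is the best case for the interaction and for the smaller sex. The larger sex gains: it reaches 81% at 14 per group and 86% at 16.

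**7. The same interaction test on the other stated effects.** Interaction equal to the full stated effect, even sex split:

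| Endpoint | Effect / SD | Per cell | SE of interaction | Power, full size | Power, half size |
|---|---|---|---|---|---|
| Hippocampal volume (Aim 3) | 0.1/0.03 = 3.33 | 10 | 0.03 × √(4/10) = 0.0190 | 99.9% | 72.7% |
| Loop gain (Aim 1) | 2.1/0.4 = 5.25 | about 32 | 0.4 × √(4/32) = 0.141 | about 100% | >99.9% |
| Word pairs (Aim 4, n = 60) | 6.9/2.2 = 3.14 | 15 | 2.2 × √(4/15) = 1.136 | >99.9% | 85% |

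The Aim 1 cell size takes the 130 completers as 65 with OSA and 65 without. For Aim 2 (20/h, SD 5/h, 65 subjects), taking the SD as that of the within-person change, full-size power is also effectively 100%. Amyloid PET is the only endpoint with a power statement that fails.

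**The case against.** **Sex is labelled exploratory.** This limits the consequence, and no primary analysis depends on it. It does not make a statement about power true.

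**The impact of sex could mean a main effect.** Comparing 20 men with 20 women on amyloid, an assumed difference of 0.2 SUVr would have about 93% power. The ambiguity is real, and the interactions that the paragraph calls important concern ApoE. But the plan states no sex effect of any size, so the claim has no calculation behind it on this reading either.

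**The split is assumed.** It is. Imbalance lowers interaction power and the smaller sex's power, so the even split is not chosen to make the plan look worse.

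**Aim 3's primary measure is hippocampal volume, which is powered.** This stands, on the effect stated. It does not rescue a claim covering all cases, because Section 10 powers amyloid separately and rests the interpretation of Aim 3 partly on it.

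**Stronger readings to avoid.** A reader might infer that Aim 3 as a whole, or every aim, lacks power for sex, on the rule that a sample sized for a main effect cannot detect an equal interaction. That rule needs main-effect power not far above 80%. The stated effects outside amyloid PET give far more, so the plan's figures do not support the inference. Even if only 20 people entered Aim 4 (roughly the 30% oxygen responsiveness quoted in Section 7 applied to 65), a full-size interaction would have about 91% power. Whether effects that large are plausible is a separate question. A reader might also think the plan contradicts itself where it says "we are not powered for brain structures beyond our primary outcomes" and, in Aim 4, "but are not powered for multiple comparisons". The first concerns other regions in a whole-brain search and the second other neurocognitive variables. Neither concerns sex.

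**Conclusion.** The sentence is wrong as written, and the matter is minor. The failure shown is confined to Aim 3 amyloid PET: about 65% power within one sex and 40% for a sex-by-OSA interaction of 0.2 SUVr, estimated only to within about 0.23 SUVr either way. These figures rest on the plan's amyloid inputs, two-sided testing, an even sex split, and reading the impact of sex as sex-specific or modifying effects. For hippocampal volume and Aims 1 and 4 the claim is uncalculated rather than contradicted by the stated effects. For tau PET it cannot be checked, because no power inputs are given.

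**What to change.** Delete the blanket power claim in the opening paragraph of Section 10 and put in its place:

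> Sex is an exploratory modifier; no sex-specific power calculation was made, and amyloid PET (20 per group) is not powered for within-sex or sex-by-OSA interaction effects of 0.2 SUVr. We will report the sex-by-group (or sex-by-treatment) interaction with 95% CI and will not infer absence of a sex difference from a non-significant test.

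The cost is a short text change in the SAP that makes a stated property less favourable. Sample sizes, visits and primary analyses stay as they are.

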Despite these recognized consequences, treatment of OSA remains unsatisfactory. Nasal PAP (positive airway pressure) is the treatment of choice for OSA based on randomized trials; its impact can be transformative for some patients. However, many patients have poor adherence to PAP or experience variable efficacy with alternative therapies such as oral appliances and upper airway surgery. Many patients avoid the diagnosis of OSA or are lost to follow-up prior to start of therapy emphasizing the need for improved OSA treatment. We have recently reported predictors of oxygen responsiveness using a cross-validated pathophysiological model, but require further data (e.g. further validation, assessment of generalizability to older cohorts) before implementation. This proposal will provide that further validation.

Importance of Aging in Sleep Apnea: The importance of aging in OSA is established. First, aging is a major risk factor for OSA. OSA has been shown to increase in prevalence with aging, in part as a function of increasing body weight. In women, menopause is also an important risk factor. Thus, aging of the population is

yielding an increasing burden of OSA. Second, some epidemiological data have suggested that the impact of OSA may be reduced with aging. That is for a given severity of OSA, the consequences of OSA may be less in older vs. younger people. However, this aging-related protection has been debated, and the purported survivor effects in OSA are likely overstated. Third, both data and clinical experience support the notion that elderly often struggle with PAP, emphasizing the need for new therapeutic approaches.

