OSA in the Elderly May be a Distinct Disease: We and others have suggested the mechanisms underlying OSA in the elderly may be different from matched younger individuals. While many OSA patients have major anatomical predisposition to OSA, i.e. elevated positive Pcrit about one third of individuals with OSA have loop gain abnormalities as a major contributing factor to their disease. Esophageal pressure measurements have shown a lower value in elderly OSA patients during respiratory events compared to younger OSA patients, suggesting an aging effect on major pathophysiological variables such as control of breathing¹⁴¹, airway mechanics or the arousal threshold. Also, central apneas increase with aging, again suggesting an underlying component of instability in ventilatory control. Sleep typically becomes more fragmented with aging, a finding of relevance to the type of unstable breathing which occurs with state transitions (i.e. CO₂ fluctuations from sleep to wake to sleep). However, other studies, including our own have not shown a major impact of aging on loop gain (or low values in older vs. younger OSA patients), emphasizing the need for further study. Because studies show loop gain elevation in some elderly (e.g. using a pressure drop or pressure support technique) whereas other studies show no major elevation of loop gain in the elderly (using a proportional assist ventilation PAV technique), interventional studies will be required to bring clarity. Of note the PAV technique relies on stable sleep and stable upper airway two assumptions which are flawed in the elderly perhaps leading to an underestimate of the breathing control abnormalities in this age group. As stated, O₂ responsiveness is not just a function of high loop gain but interacts with other OSA endotypes. Based on available data we estimate ~30% of elderly OSA patients should be O₂ responsive.

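### The Aim 2 interpretation lets a finding that many patients respond to oxygen stand as evidence that responders can be predicted, and no stated analysis can show that the prediction fails

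*Combined protocol and SAP*

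**What the plan says.** Section 7 explains that the endotype-based model of oxygen response needs more validation, including in older cohorts, and promises: "This proposal will provide that further validation". It also gives the expected frequency of response: "Based on available data we estimate ~30% of elderly OSA patients should be O₂ responsive".

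Section 6 (Aim 1) plans to assess predicted response to oxygen, and Hypothesis 1 concerns the proportion predicted to respond. Section 10 (Aim 1) says the predictors of responsiveness will be assessed, and gives no method.

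For Aim 2, Section 10 compares AHI on oxygen with AHI on room air across patients with differing endotypes. It is powered "with a change in AHI of 20/h (a clinically important difference) with standard deviation 5/h". Section 11 gives the number: "65 subjects who have been identified to have obstructive sleep apnea will complete Overnight visit #2-#3".

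The interpretation follows. It opens "The interpretation should be straightforward" and continues "If we confirm a major subset of OSA patients who are oxygen responsive, we will extend our recent findings that we can identify these patients" from their pathophysiology. Later in the same section the plan recalls that "the combination of endotypes determined oxygen response with 83% accuracy in our pathophysiological model which we are working to validate further".

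**The concern.** Prevalence and discrimination are separate properties. Response can be common while the model picks responders no better than chance, and it can be rare while the model picks them well. The sentence goes from the first property to the second with no term for model performance.

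The rest of the interpretation does set out contrary outcomes: oxygen may fail to lower loop gain, or may lower loop gain without improving AHI. It has none for the case where responders exist and the endotypes do not identify them.

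What is at stake is the validation in older patients that Section 7 promises. Prediction may also matter downstream. Section 11 reserves Aim 4 for 60 oxygen-sensitive participants and Section 9 for those identified to benefit from oxygen, though neither says how they are identified. The primary AHI comparison of Aim 2 is not affected.

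**Working it through.** **1. The plan's own figure.** The only design figure for Aim 2 is power above 0.8 at alpha 0.05 for a mean AHI change of 20/h with SD 5/h. I assume a two-sided paired t-test (noncentral t).
- If 5/h is the SD of the change, the standardised effect is 20/5 = 4, and n = 3 gives power 0.91.
- If 5/h is the SD of one night and the nights are uncorrelated, the SD of the change is 5√2 = 7.07, and n = 4 gives power 0.95.

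So the statement holds with 65 patients. It concerns the mean change only and says nothing about prediction.

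**2. Inputs to the condition.** n = 65 (Section 11) and true responder rate p = 0.30 (Section 7). The cut-off c that would define a major subset is not in the documents, so a range is assumed.

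**3. Chance that the condition is met.** With X ~ Binomial(65, 0.30) and r equal to 65c rounded up, the chance is P(X ≥ r):

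| Assumed cut-off c | 65c | r | P(X ≥ r) |
|---|---|---|---|
| 15% | 9.75 | 10 | 0.998 |
| 20% | 13 | 13 | 0.975 |
| 25% | 16.25 | 17 | 0.79 |
| 30% | 19.5 | 20 | 0.49 |
| 33% | 21.45 | 22 | 0.29 |
| 40% | 26 | 26 | 0.055 |
| 50% | 32.5 | 33 | 0.0004 |

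Model performance does not enter the formula. Each row is therefore the same whatever the model's AUC.

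**4. Simulation of the contrast.** 20,000 runs per AUC, n = 65, 30% responders, binormal score, cut-off 25%. The second column adds a Mann-Whitney test that AUC exceeds 0.5 (critical z 1.96).

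| True AUC | Condition as written | Condition plus AUC test |
|---|---|---|
| 0.5 | 79% | 2% |
| 0.6 | 79% | 20% |
| 0.7 | 79% | 60% |
| 0.8 | 79% | 78% |
| 0.9 | 79% | 79% |

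The second column cannot exceed 79% because the prevalence condition is kept in it.

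**5. The accuracy benchmark in this cohort.** If 30% respond, calling everyone a non-responder is right in 1 − 0.30 = 70% of cases. Flagging 30% at random is right in 0.30² + 0.70² = 0.09 + 0.49 = 58%. To show accuracy above 70% with 65 patients, a rule of at least 52 correct (52/65 = 80%) has one-sided alpha 0.048, and power 0.79 if true accuracy is 83%. An observed 54/65 (83%) has an exact 95% CI of 72% to 91%.

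**6. Why the definition of response matters.** If 5/h is the SD of the change and changes are normal, the power inputs imply that 97.7% of patients improve by more than 10/h (z = (10 − 20)/5 = −2) and 84% by more than 15/h (z = −1). The estimate of about 30% must then rest on a stricter or different definition, and the documents do not give one.

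**The case against.** **The sentence may be a plan of work.** To extend the findings could mean that, given enough responders, the investigators will go on to study prediction. Section 10 uses the verb that way when it says the predictors will be assessed so as to extend recent publications. The reading is possible. It fits poorly with the surrounding sentences, which go from a result to a conclusion. It also leaves the gap open, because the validation analysis is still unstated.

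**The topic is not omitted.** A reader might infer that the plan ignores validation or treats the model as proven. The documents do not support that. Sections 6, 7 and 10 announce an assessment of the predictors, describe the model as still being validated, and say changes in loop gain will be read alongside the other endotypes. What is missing is a comparison of predicted with observed response and a criterion for it.

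**The condition is not bound to be met.** A reader might infer that it is met almost automatically. That is true only for cut-offs below the plan's own 30%. At 30% it is about even, and at 40% it is unlikely.

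**The 83% cannot be discounted against 70%.** The 83% comes from an earlier cohort whose responder rate the documents do not give. The 70% benchmark applies only to the new elderly cohort.

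**Details may lie elsewhere.** The cited publication may give the model, its cut-off and a definition of response. It was not available here, and the plan does not say that it adopts them.

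These points narrow the concern to the inference and the missing criterion. That much stands.

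**Conclusion.** The point holds in this limited form: Section 10 rests a discrimination claim on a prevalence result, and no result is named under which validation fails. The defect is logical and does not depend on any cut-off. Its numerical expression does: 0.998 down to 0.055 for cut-offs of about 15% to 40%, given 65 patients, a 30% responder rate and independent patients.

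A reader might go further and infer that a useless model will be reported as validated. The text permits that conclusion but does not commit the investigators to it. The change should be made before the Aim 2 nights are analysed.

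**What to change.** Replace the sentence in Section 10 with a rule that uses model performance:

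1. Define AHI response in advance.
2. Lock the existing model and its cut-off.
3. Compute each OSA patient's prediction from Overnight 1 polysomnography before Overnights 2 and 3 are scored. Say how participants with only a home sleep test are handled: Sections 9 and 21 allow that substitution, and the documents do not say that endotypes can be derived from it.
4. Cross predicted with observed response. Report AUC, sensitivity and specificity with 95% CIs, beside the no-information accuracy in this cohort (about 70% if 30% respond).
5. State that prediction is better than chance only if the lower limit for AUC exceeds 0.5. That shows ranking and does not by itself show that patients can be identified. Make the identification claim only with the sensitivity and specificity intervals shown and accuracy above the no-information rate.
6. Report the responder proportion as a separate result.
7. State that if responders exist but the criterion is not met, the model is not validated in this population.

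The cost is SAP wording and one analysis, with no added visits. There are two downsides. The validation claim can now fail. And 65 patients give only moderate power for the accuracy criterion (0.79 in the example above), so a failure should be reported with its intervals and not taken as proof that the model has no value.
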